### At 365 ± 14 days following the first and final islet infusion:

- The proportion of subjects with full islet graft function
- The proportion of subjects with an HbA1c <7.0% and free of severe hypoglycemic events from day 28 through day 365
- The percent reduction in insulin requirements

- HbA1c
- MAGE
- LI
- Clarke score
- HYPO score
- Basal (fasting) and 90-min glucose and C-peptide (MMTT)
- β-score
- C-peptide:glucose creatinine ratio
- Acute insulin response to glucose (AIRglu), insulin sensitivity, and disposition index derived from the insulin-modified frequently-sampled intravenous glucose tolerance (FSIGT) test
- Glucose variability and hypoglycemia duration derived from the continuous glucose monitoring system® (CGMS)
- The proportion of subjects receiving a second islet infusion
- The proportion of subjects receiving a third islet infusion

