## 5.15.3 Premature Discontinuation of Study Treatment

Study treatment may be prematurely discontinued for any subject for any of the following reasons:1.

The subject is unwilling or unable to comply with the protocol.2. The investigator believes that the study treatment is no longer in the best interest of the subject.3. Graft Failure: Islet allograft failure will be defined as absence of insulin production by transplanted islets, as evidenced by absence of c-peptide <0.1nmol/L (<0.3 ng/mL). This will be determined by (1) c-peptide <0.1nmol/L (<0.3 ng/mL) on random testing, followed by (2) c-peptide<0.1nmol/L (<0.3 ng/mL) at baseline, and at 60 and 90 minutes after MMTT. C-peptide levels obtained in the course of the MMTT levels will be run at the core laboratory in Seattle, WA. Subjects with graft failure do not need to complete the day 75 metabolic assessments.

4. A unexpected related serious adverse event. The agent(s) to which the event is attributed will be discontinued.

Subjects who prematurely discontinue study treatment will remain in the study until normal termination, for the purpose of monitoring safety and efficacy parameters and will enter the reduced

schedule outlined in Appendix 2. Data from these subjects will be used in the intent-to-treat analysis. 6. Criteria for Premature Termination of the Study

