#### 7.4.2 Criteria and Timing for Subsequent Islet Transplant

If repeated transplantation (s) are needed the subject will follow the same protocol and will remain in the randomized study group previously assigned. Subjects who do not meet criteria for a subsequent transplant will enter the reduced follow-up schedule (Appendix 2).

**Partial Graft Function:** Islet transplant recipients who do not meet criteria for full islet graft function, but have either a basal or stimulated c-peptide level  $\geq 0.1$  nmol/L ( $\geq 0.3$ ng.mL), will be considered partial islet graft function.

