#### 9.1.1.7 THE C-PEPTIDE TO GLUCOSE, CREATININE RATIO

The C-peptide to glucose, creatinine ratio (CPGCR) will be determined from the fasting (basal) glucose and c-peptide, and a simultaneous serum creatinine. This measure accounts for both the dependence of c-peptide secretion on the ambient glucose concentration and the dependence of c-peptide clearance on kidney function. The CPGCR is calculated as [c-peptide (ng/mL) \* 100]/ [glucose (mg/dL) \* creatinine (mg/dL)]. An index of islet graft function, this measure correlates well with both the 90-minute glucose levels during a MMTT and with the  $\beta$ -score.

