#### **10.2.2 SECONDARY ENDPOINTS**

The secondary endpoints are defined in section 3.1.2.

HbA1c levels will be categorized for example, as either normal (<= 7.0 %), or non-normal (>7.0%). Dichotomous variables such as HbA1c (normal/non-normal) and rate of severe hypoglycemic events will be analyzed using logistic regression analysis with a term for treatment. Should a dichotomous endpoint not be evaluated for a particular individual then a failure will be imputed unless an evaluation is done at a time longer than 75 days after transplant and before an additional islet cell infusion, in which case that later value will be imputed.

Continuous variables such as QOL scales will be analyzed by a t-test. If there is compelling evidence that the normal distribution does not hold then a logarithmic or square root transformation will be done before using the t-test. If lack of normality persists, non-parametric tests will be used.

By examining multiple secondary endpoints it is likely that some variables will be found significantly different between the two treatment groups, but these findings may be Type I errors. Appropriate qualifiers will be reported with any significant secondary findings.

Regression models for longitudinal data (mixed models) will be used to examine the differences between groups in each of the response variables (HbA1c level and C-peptide levels) where measurements are repeated over time. Mixed models for dichotomous variables will be used to model full islet graft function over time. Survival analysis models will be used to compare time to becoming insulin dependent and to identify risk factors through Kaplan-Meier estimates and Cox regression models.

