## APPENDIX 2. REDUCED FOLLOW-UP SCHEDULE

Subjects withdrawn from study therapy should be followed according to the reduced follow-up schedule provided below. All reduced follow-up assessments should be scheduled relative to the day on which the study treatment is discontinued. The last follow-up visit will vary depending on when the subject discontinues study therapy and should be done at 1-year post the subject's **last** transplant.

Complete the following assessments at the intervals (+/- 7 days) indicated below relative to the day the subject discontinued study treatment. Continue conducting these assessments at the defined intervals until the subject reaches one year post **last** transplant.

- Assess SAEs and hypoglycemic events: q1 month. If subject does not come to the study site for the visit, attempt to obtain information via a phone contact.
- Alloantibody (central lab): q 1 month for the first 3 months and q 3 months thereafter.

Complete the following assessments at 1-year (+/- 14 days) post initial transplant:

- Assess SAEs and hypoglycemic events
- Alloantibody (central lab)
- HbA1c (central lab)
- 90 minute c-peptide post MMTT (central lab)
- Serum creatinine (central lab)
- QOL questionnaire (via mail or in-person)

Complete the following assessments at 1-year (+/- 7 days) post **last** transplant:

- Assess SAEs and hypoglycemic events
- QOL questionnaire (via mail or in-person)

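### The reduced follow-up schedule does not call for the fasting sample, glucose or insulin dose that several Day-365 secondary endpoints need in subjects who stop treatment

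*Protocol*

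**What the plan says.** **Who goes onto the reduced schedule.** Protocol 5.15.3 allows treatment to be stopped for non-compliance, investigator judgment, graft failure or an unexpected related serious adverse event. It says: "Subjects who prematurely discontinue study treatment will remain in the study until normal termination, for the purpose of monitoring safety and efficacy parameters". These subjects follow Appendix 2, and "Data from these subjects will be used in the intent-to-treat analysis". Section 7.4.2 adds a second route: "Subjects who do not meet criteria for a subsequent transplant will enter the reduced follow-up schedule (Appendix 2").

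**What Appendix 2 collects.** At one year after the initial transplant it lists safety and hypoglycemia, alloantibody, HbA1c, "90 minute c-peptide post MMTT (central lab"), "Serum creatinine (central lab") and a quality-of-life questionnaire. At one year after the last transplant it lists only safety and hypoglycemia, and quality of life.

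**What the Day-365 endpoints need.** Section 4.1.3 sets the Day-365 endpoints after both the first and the final infusion. They include "Basal (fasting) and 90-min glucose and C-peptide (MMTT"), percent insulin reduction, the beta-score and CPGCR. Under 9.1.1.7 the CPGCR "will be determined from the fasting (basal) glucose and c-peptide, and a simultaneous serum creatinine". Under 9.1.1.6 the beta-score uses HbA1c, insulin requirement, fasting glucose and stimulated C-peptide.

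**How they are analyzed.** Section 10.2.2 says "Continuous variables such as QOL scales will be analyzed by a t-test". It imputes failure for unevaluated dichotomous endpoints and gives no corresponding rule for continuous ones.

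**The concern.** The protocol says that stopped subjects are followed for efficacy and analyzed as randomized, but the schedule it puts them on does not request the measurements that several efficacy endpoints are made of. An analysis plan can choose how to handle a missing value. It cannot restore a glucose result or an insulin dose that was never captured.

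The gap is not random with respect to outcome. Graft failure is one of the reasons for stopping, and LMW-DS is meant to improve engraftment. If the arms differ in how many subjects stop, the affected comparisons could be made on groups selected after randomization. Section 5.15.3 also waives the Day-75 metabolic assessment for graft failures, so these subjects may have few earlier post-transplant values to inform an imputation.

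**Working it through.** This point rests on no figure stated in the plan. The main check compares the Appendix 2 items with the components of each endpoint.

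**Step 1. Component check**

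| Day-365 endpoint | Components needed | Listed, 1 year after initial transplant | Listed, 1 year after last transplant |
|---|---|---|---|
| Fasting C-peptide | 1 | 0 | 0 |
| Fasting and 90-minute glucose | 2 | 0 | 0 |
| CPGCR | 3 (fasting glucose, fasting C-peptide, creatinine) | 1 (creatinine) | 0 |
| Beta-score | 4 (HbA1c, insulin dose, fasting glucose, stimulated C-peptide) | 2 (HbA1c, 90-minute C-peptide) | 0 |
| Percent insulin reduction | post-transplant insulin dose | 0 | 0 |
| HbA1c | 1 | 1 | 0 |
| 90-minute C-peptide | 1 | 1 | 0 |

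The first five rows cannot be built from the listed items at either anniversary. The last two can be built at the first anniversary only. For a subject with a single transplant the two anniversaries coincide and the fuller list applies. The post-last-transplant gap therefore concerns subjects who were re-transplanted and then moved to Appendix 2.

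**Step 2. Could the data arrive by another route?**
- The only mixed-meal test the protocol defines (9.1.1.5) draws fasting glucose and C-peptide, then samples at 15, 30, 60, 90 and 120 minutes. A test run that way would produce the fasting and 90-minute values, but Appendix 2 asks for one of them.
- Subjects keep glucose and insulin notes until the study ends (7.6; also 9.1.1.1). Section 7.6 ties diary collection to the Schedule of Events, which is Appendix 1. Appendix 2 names no diary, glucometer download or insulin dose.

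The protocol therefore leaves capture unspecified. It does not show that the data are absent.

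**Step 3. Illustration of what could be hidden (assumed values)**

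Let *m* be the mean in on-schedule subjects, taken as equal in both arms, and *s* the mean in stopped subjects. Let *f* be the number stopped of 18 per arm (10.4).

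All-randomized difference = (*m* − *s*) × (*f* control − *f* LMW-DS) / 18. The difference among on-schedule subjects is 0 by assumption.

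| Stopped, control vs LMW-DS | Insulin reduction, *m* = 80%, *s* = 0% | Insulin reduction, *m* = 80%, *s* = 40% | Beta-score, *m* = 5, *s* = 0 |
|---|---|---|---|
| 3 vs 1 | 80 × 2/18 = 8.9 points | 40 × 2/18 = 4.4 | 5 × 2/18 = 0.56 |
| 6 vs 2 | 80 × 4/18 = 17.8 points | 40 × 4/18 = 8.9 | 5 × 4/18 = 1.11 |
| 6 vs 1 | 80 × 5/18 = 22.2 points | 40 × 5/18 = 11.1 | 5 × 5/18 = 1.39 |

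Equal numbers stopped give 0, and more stops on LMW-DS reverse the sign.

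**Step 4. Loss of precision, for context**

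Section 10.4 states 90% power for a difference of 1.0 nmol/L with SD 0.9 and 18 per arm. The exact noncentral t calculation has noncentrality (1.0/0.9) × √(18/2) = 3.33 on 34 degrees of freedom and gives 0.899, so the stated figure is reproduced. At the same standardized difference of 1.11, power is 0.836 with 15 per arm and 0.739 with 12. These values describe the primary-endpoint design. The standardized differences for the affected secondary endpoints are not given.

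**The case against.** **Data may still be captured.** A reader might infer that the fasting values and insulin doses do not exist for these subjects. The documents do not support that. The Appendix 2 line may name the result to be reported from a standard test, and diaries continue to study end. What stands is that Appendix 2 calls for neither to be captured.

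**Graft loss is seen elsewhere.** A reader might infer that the Day-365 continuous comparisons as a whole lose any benefit from preventing graft loss. They do not. HbA1c and 90-minute C-peptide are both collected at one year after the initial transplant, and the latter is the most direct continuous measure of graft loss. Dichotomous endpoints impute failure (10.2.2), and the Day-75 primary has its own imputation rule (10.2.1).

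**The remaining comparison is not simply one of surviving grafts.** Failed grafts that are re-transplanted restart full follow-up (7.5, 7.7). Stops also happen for reasons other than graft failure, and subjects with partial function who are ineligible for a further transplant also move to Appendix 2. The accurate description is subjects still on the full schedule, probably enriched for functioning grafts.

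**Complete-case analysis is not stated.** Section 10.2.2 does not say that stopped subjects are left out, and handling of missing continuous endpoints may sit in the SAP, which was not available. For confirmed graft failure an SAP could assign some values: C-peptide is below 0.1 nmol/L by definition, and a beta-score of 0 denotes no graft function. That does not extend to glucose or insulin dose, nor to stopped subjects who retain partial function.

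**A lighter schedule is legitimate.** Dropping demanding tests such as the FSIGT and CGMS for people off treatment is a reasonable choice. This point is confined to endpoints that a test already on the schedule, plus a diary entry, would supply.

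**Conclusion.** The point holds as a gap in specified data collection for secondary endpoints. As listed, Appendix 2 cannot supply fasting C-peptide, fasting or 90-minute glucose, CPGCR, beta-score or percent insulin reduction at one year after the initial transplant. At one year after the last transplant it supplies no metabolic endpoint, although 4.1.3 sets the same endpoints there. This sits badly with the efficacy and intent-to-treat statements in 5.15.3.

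For the affected endpoints, missingness is linked to stopping treatment, including for graft failure, and the comparisons may be selective. The size and direction of any bias are unknown. The 4.4 to 22.2 points of insulin reduction and 0.56 to 1.39 beta-score units in the illustration rest entirely on assumed means, equal on-schedule performance and assumed stopping counts. The primary endpoint and its conclusion are not touched. This is a worthwhile, inexpensive improvement and does not threaten the trial's main result.

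**What to change.** **One year after the initial transplant.** In Appendix 2, replace the mixed-meal test item with fasting and 90-minute glucose and C-peptide from that test, and add total daily insulin dose taken from the diary. Compute CPGCR (with the creatinine already listed) and beta-score (with the HbA1c already listed) from these, and include these subjects in the Day-365 comparisons.

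**One year after the last transplant.** Either collect the same metabolic items there, or state that these endpoints are not assessed at that time in subjects on the reduced schedule and how those subjects enter the analysis.

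**Cost.** At the initial-transplant anniversary: one fasting sample and the glucose assays at a test already scheduled, plus one diary item, with no new visit. If the full mixed-meal sampling was always intended, that part is a wording change only. Extending the post-last-transplant visit costs somewhat more, because Appendix 2 schedules no mixed-meal test there and allows the questionnaire by mail.
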